9.2 Patient demographics and other baseline characteristics

All data for background and demographic variables will be listed by treatment group and patient. Summary statistics will be provided by treatment group.

Relevant medical history, current medical conditions, results of laboratory screens, drug tests and any other relevant information will be listed by treatment group and patient.

9.3 Treatments (study drug, rescue medication, other concomitant therapies, compliance)

Data for study drug administration (rescue medication) and concomitant therapies will be listed by treatment group and patient.

9.4 Analysis of the primary variable(s)

The primary aim of this study is to determine the effect of a single injection of CGF166 on pure tone audiometry measured at 4 week intervals from month 1 to month 6 after surgery. The second primary objective is to assess the safety and tolerability of IL CGF166.

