Investigational and reference therapy	 CGF166 is recombinant adenovirus 5 (Ad5) vector containing the human Atonal transcription factor (Hath1) cDNA. CGF166 will be provided in a septum vial, containing 0.5 mL Commercially of opalescent liquid viral vector. In Part A and Part B all investigational infusion volume was infused at a rate of 10 µL/min except 1 patient where in fusion volume was infused at a rate of 20 µL/min. In Part C all following protocol amendment 5 all investigational infusion volumes will be infused at a rate of up to 10 µL/min in to the perilymphatic space 						
Efficacy	litory assessments						
assessments	 Pure tone audiometry, including immittance testing Speech audiometry Brainstem auditory evoked response evaluations (BAER) 						
	Vestibular assessments						
	Head Impulse test						
	Commercially Confidential Information						
Safety assessments	 Physical examination Otoscopy 						
	 Neurological exam FSH verification and Pregnancy test (serum at screening and urine at subsequent visits) 						
	 Vitals and body measurements (height, weight, temperature, blood pressure, and pulse rate) 						
	• ECG						
	Clinical laboratory tests (hematology, chemistry, and urinalysis)						
	MRI with gadolinium (within 3 months or performed at screening)						
	Adverse events						
Other assessments	Commercially Confidential Information						

Data analysis	 Tone thresholds will be analyzed for each frequency tested separately.
	 Pure tone audiometry air conduction threshold data will be listed and graphically displayed by patient, infusion volume, frequency, and visit/time.
	 Summary statistics will be provided by infusion volume, frequency, ear and visit/time.
	 Change from baseline of the thresholds (mean of screening and baseline visit) will also be summarized by infusion volume, frequency, ear and visit/time
Key words	Hearing loss, cochlear implant, gene therapy

Assessment schedule

Study Phase	Screening visit	Baseline	Treatm ent day	Post-op O	bserv	ation	period			Follow -u				End of Study⁵
	Day -63 to -4	Day -3 to -1		Day 1			Day 4	Day 6	Day 15	Day 29	Day 57	Day 113	Day 169	
Visit Num bers	1	2		3		4	5	6	7	8	9	11	13 / 777	777
Time (h)			pre-infusion	Post-infustion	4 hr									
Inclusion/Exclusion	x	x												
Relevant medical history/Current medical conditions	x	x				as needed								
Demography	х													
Auditory and vestibular function assessments	x	x								x	x	x	x	x
	Con	nmercially C	confidential Info	ormation										

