History of alcohol and drug dependence	x	·								x				
General Physical exam	x	x												
Otoscopy	х	x							х	х	х	х	х	x
Neurological evaluation	x	x				х	х	х	х	х	х	х	х	x
Pregnancy test	x (serum)	x											X ⁶	x
HIV and Hepatitis	x													
Vitals Signs and body measurements														
Body Height	х													
Body Weight	x	x									х	х	х	x
Body Temperature Blood pressure / Pulse	x	x				х	х	x	х	х	х	х	х	x
rate	x	x				х	х	x	x	x	x	x	x	x
ECG	x	x				х					х	х	x	x
Hem atology, Blood chem istry, Urinalysis	x	x				x	x		x		x	x	x	x
1	Cor	nmercially (Confidential Inf	ormation						-				
	Comr	nercially Co	onfidential Infor	mation										
⁵ - Pts. Who have com ple in the study will com plet	ted Day 169 in	the study wi	ill return to site a	s soon as possb	ile an	d com	plete e	end of	study vis	it 777; Pa	tients w	ho have n	iot com pl	eted Day 169
⁶ - assessment done if it				-										

Novartis
Amended Protocol Version v06 (Clean)

Study Phase	Screening visit	Baseline Day -3 to -1	Treatment day	Post-op Observation period					Follow-up Period					End of Study⁵
	Day -63 to -4		Day 1			Day 2	Day 4	Day 6	Day 15	Day 29	Day 57	Day 113	Day 169	
Visit Numbers	1	2	3		4	5	6	7	8	9	11	13 / 777	777	
MRI with gadolinium	x										X ³	X ³	X ³	x
C-SSRS		х								х	х	х	х	х
Comments	as needed													
Adverse events	as needed													
Concomitant meds/Therapies	as needed													
Study Surgery			x											
Dose administration			х											
Study Completion													X ⁶	х

Commercially Confidential Information

C-SSRS- Columbia Suicide Severity Rating Scale; Commercially Confidential Information

³ MRI may be performed if the audiometery meets one of the stopping criteria

Commercially Confidential Information

⁵ - Pts. Who have completed Day 169 in the study will return to site as soon as possbile and complete end of study visit 777; Patients who have not completed Day 169 in the study will complete end of study (visit 777) assessment on Day 169

⁶ - assessment done if it is end of study assessment.

1 Introduction

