Eligible patients will return to the study center at baseline (Day -3 to -1) and undergo pre-operative preparation as well as pre-treatment functional assessments.

Day 1 visit

On Day 1, study patients will undergo the required protocol assessments and the stapedotomy for delivery of the study drug to the scala vestibuli perilymphatic space of the inner ear. At the completion of the surgery and study drug infusion, study patients will recover in the surgical center's post-op facility and undergo post-surgery evaluations and assessments. Study patients may be transitioned to either the inpatient unit of the surgical center or pre-arranged temporary housing close to the surgical center.

Day 2 to Day 6 visits

Study patients will be followed up for the next 5 post surgery days (Day 2 to Day 6) and will undergo the protocol-required safety follow up evaluations. Study patients will be discharged home if there are no significant adverse events requiring prolonged monitoring. Patients will have the option to remain in the provided housing until the completion of the Day 14 visit.

Subsequent visits will be scheduled with the study patients prior to being discharged.

Day 15 visit

Study patients will return to the study center to have surgical packing removed from their ear and will also undergo study required assessments. Patients will be discharged home or to their local housing at the end of all study required evaluations. Patients will be reminded of their next scheduled visit.

Follow up and end of study visits

Total follow-up period in the trial will be 6 months after administration of CGF166. The follow-up visits will be at 2, 4, and 6 months/EOS.

Patient who have already completed Day 169 assessment ($\sim 6 \text{ month}$) will return to site to complete end of study visit (visit 777) as soon as practically possible. Patients who have not completed Day 169 will complete end of study visit (visit 777) on Day 169.

During each visit to the study center, post-operative recovery of the study ear will be monitored and evaluated. Study patients will also undergo the study-required safety, Confidential Information

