5.5.13 Early study termination

The study can be terminated at any time for any reason by Novartis. Should this be necessary, the patient should be seen as soon as possible and treated as a prematurely withdrawn patient. The investigator may be informed of additional procedures to be followed in order to ensure that adequate consideration is given to the protection of the patient's interests. The investigator will be responsible for informing IRBs and/or ECs of the early termination of the trial.

6 Visit assessments

The full Assessment schedule is presented at the end of the synoptic section, above.

Patients should be seen for all visits on the designated day or as close to it as possible.

Patients who discontinue study before completing the study, and those who prematurely withdraw from the study for any reason, should be scheduled for a visit as soon as possible, at which time all of the assessments listed for the final visit will be performed.

Acceptable deviations ranges from assessment times based on logistical and operational considerations are detailed in separate data management module documents.

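### Does the primary audiometry aim, stated as 4-weekly from month 1 to month 6, need correcting because the visit schedule has 8-week gaps after Day 57?

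*Protocol*

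**What the plan says.** Protocol Section 9.4 and SAP Section 7.1 use the same words for the primary efficacy aim: the effect of a single injection on "pure tone audiometry measured at 4 week intervals from month 1 to month 6 after surgery". Neither names study days.

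The protocol's assessment schedule, in the row "Auditory and vestibular function assessments", marks screening, baseline, Days 29, 57, 113 and 169, and End of Study. The visit numbers for the four dated post-dose days are 8, 9, 11 and 13, the last shown as 13 / 777. There is no visit 10 or 12.

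Protocol Section 3.1 gives a shorter list: "The follow-up visits will be at 2, 4, and 6 months/EOS".

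On the final visit, footnote 5 of the schedule says "Patients who have not completed Day 169 in the study will complete end of study (visit 777) assessment on Day 169". Section 3.1 says that patients already past Day 169 "will return to site to complete end of study visit (visit 777) as soon as practically possible". Protocol Section 6 adds that patients who stop early "should be scheduled for a visit as soon as possible, at which time all of the assessments listed for the final visit" are to be done. The same section says "Patients should be seen for all visits on the designated day or as close to it as possible", and that "Acceptable deviations ranges from assessment times based on logistical and operational considerations are detailed in separate data management module documents".

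For analysis, Protocol 9.4.2 plans listings, graphs and summary statistics by visit or time. SAP 7.1.2 mentions listings and graphs only. SAP Section 1.1 places derivation rules in Module 8 of the analysis plan, which is not among the documents here.

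**The concern.** The sentence that defines when the primary variable is measured describes a denser design than the one being run. A reader of Section 9.4 would look for results near months 3 and 5. Finding none, the reader might take them for missing data rather than visits that the current schedule does not contain. Section 3.1 makes matters worse with a third version that leaves out Day 29.

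The number 777 raises a second question. It stands for Day 169 in patients who have not yet completed that visit, and for an undated later recall in those who have. If summaries were keyed on visit number, Day 169 values could be split between 13 and 777, and late recalls could be averaged with on-time values. The 30 µL group could hold both kinds: Protocol Section 5.2 lists 40 or 30 µL for Cohort 2, in the completed Part B, and 30 µL for Cohort 5 in Part C. At stake would be how clearly the hearing results over time can be read.

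**Working it through.** **Inputs.** Stated interval of 4 weeks, months 1 to 6 (Protocol 9.4, SAP 7.1). Scheduled post-dose auditory days 29, 57, 113 and 169 (assessment schedule). Dosing on Day 1.

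**Grid implied by the stated interval.** Day = 1 + 7 × week. Weeks 4, 8, 12, 16, 20 and 24 give Days 29, 57, 85, 113, 141 and 169, which is six points.

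**What is scheduled.** Four of the six; Days 85 and 141 are absent. The intervals are:

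- 57 − 29 = 28 days = 4 weeks
- 113 − 57 = 56 days = 8 weeks
- 169 − 113 = 56 days = 8 weeks

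The stated 4-week interval therefore holds for one gap in three. End of Study adds no point inside months 1 to 6: it is Day 169 for patients who have not completed that day, and later for the rest.

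**Visit numbers.** Counting one visit every 4 weeks from visit 8 = Day 29 gives 9 = Day 57, 10 = Day 85, 11 = Day 113, 12 = Day 141 and 13 = Day 169. The schedule has 8, 9, 11 and 13 on exactly those days. This suggests that the sentence was written for a fuller schedule, but the documents do not say so.

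**Section 3.1.** In 4-week months after dosing, Day 57 is (57 − 1)/28 = 2, Day 113 is (113 − 1)/28 = 4 and Day 169 is (169 − 1)/28 = 6. The list of months 2, 4 and 6 thus agrees with the schedule apart from leaving out Day 29.

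**Does any analysis step depend on the number of points?**

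- Protocol 9.4.2 treats each frequency separately and describes results by visit or time. No model, contrast or test uses the spacing. A table or graph laid out that way shows whatever visits took place.
- Protocol 9.4.3 and SAP 7.1.3 leave a value missing when no test was made. The only imputed values are thresholds above the machine's limit, and those require a test. No figure can be created for Day 85 or Day 141.

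**Visit 777.** The Day 169 column carries both numbers (13 / 777), and the later recall has its own End of Study column. Footnote 5 says which patients belong in which. Separating on-time from late values needs only the study day, and every air-conduction value is also listed and graphed by patient.

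**The case for a change.** The strongest case for a change is that this sentence fixes the timing of a primary variable, appears in both documents and contradicts the current schedule. All the conflicting text is in force, and putting it right would cost only a few words. A reader could also combine the sentence with the missing-data rule, under which tests not made are treated as missing at random, and count two unscheduled visits per patient as missing.

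The contradiction stands, and the arithmetic is not in doubt. The consequence does not. With no model, the missing-at-random label drives no calculation, and the schedule shows which visits were due.

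Nor can it be said that month 3 and month 5 data will not exist. Protocol Section 5.2 says that Parts A and B are complete. If an earlier schedule was fuller, as the skipped visit numbers hint, some of those patients may have Day 85 and Day 141 audiometry. Replacing the sentence in both documents with four fixed days could then leave such data without a stated place, whereas summaries by visit or time accommodate them. The SAP also describes a different design (four Part B cohorts and 20 to 30 Part C patients, against three cohorts and 10 patients in the protocol), so its wording may come from an older plan.

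On visit 777, mixing would occur only if programmers ignored the schedule's columns and the study day. The visit windows and Module 8, which would show the rule used, are held elsewhere. Their absence here is not evidence that no rule exists.

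**Conclusion.** The wording is inaccurate for the current schedule: six time points implied, four scheduled, and two of three gaps at 8 weeks rather than 4. That is the full size of the problem. It measures a mismatch in wording, not an effect on any result. Sites follow the assessment schedule, the efficacy analysis is descriptive, and no error rate, sample size or estimate changes whichever wording stands. This is a clerical slip and calls for no change to the plan.

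The visit 777 question is a gap that analysts fill sensibly: count an on-time final visit as Day 169 and show later recalls by time since dosing. Its effect cannot be sized from the documents.

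This conclusion assumes that the schedule governs conduct, as Section 6 indicates, and that no inferential analysis over time has been specified in text not available here. A model fitted across visits, or a test at a named month, would need its time points stated exactly.

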9.4.1 Variable(s)

The primary analysis variable is the audiometric threshold measured on a dB HL (hearing loss) scale at these frequencies: 0.125, 0.25, 0.5, 1, 2, 3, 4, 6, 8, 10, 12.5, 14, 16 kHz.

9.4.2 Statistical model, hypothesis, and method of analysis

Tone thresholds will be analyzed for each frequency tested separately.

For pure tone audiometry, a measure that depends on a patient being able to hear a tone, the following imputation will be done: If a patient is unable to hear the tone at a specific frequency it can be inferred that the threshold value exceeds the upper limit of the machine. In this case the value will be imputed to 5dB above the upper limit of the machine.

All pure tone audiometry air conduction threshold data will be listed and graphically displayed by patient, infusion volume, frequency, and visit/time. Summary statistics will be provided by infusion volume, frequency, ear and visit/time. Change from baseline of the thresholds (mean of screening and baseline visit) will also be summarized by infusion volume, frequency, ear and visit/time.

In addition, safety and tolerability is a co-primary endpoint, and will be analyzed as in Section 9.5.2 (Safety).

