4.1 Inclusion criteria

Patients eligible for inclusion in this study have to fulfill **all** of the following criteria:

- 1. Written informed consent must be obtained before any assessment is performed.
- 2. For all Parts (A, B and C) of the study, male or female patients, 18 to 75 years old, inclusive, with severe-to-profound bilateral or unilateral hearing loss with intact vestibular function. Non-fluctuating severe-to-profound hearing loss is required for the study ear and is defined as:

Confidential

- PTA within 10 dB of the PTA obtained at least 11 months previously.
- Word recognition within 20% of previous test at least 11 months previously [AAO-HNS Hearing Classification System]
- 3. Candidate ear ("study ear"): Minimal residual hearing based on the pure tone average of 0.5, 1, 2, and 4 kHz thresholds of ≤110 dB HL
- 4. Candidate ear ("study ear"): Pure tone audiometric thresholds of ≥50 dB HL for each testable octave frequency of 0.125 and 0.250 kHz, ≥ 70 dB HL for each testable octave frequency from 0.5 through 8 kHz and sentence recognition scores ≤50% at screening. Subject responses will be monitored for vibrotactile sensation, particularly for the low-frequency stimuli (e.g., 125 and 250 Hz). A frequency that elicits vibrotactile responses at levels below 70 dB HL will be considered "not testable" for hearing threshold and only those frequencies that are testable for hearing threshold will be considered for patient inclusion/exclusion in the study.
- 5. Patients with intact vestibular function in at least one ear (non-study ear) as measured by vestibular evoked myogenic potential (VEMP)
- 6. Able to communicate well with the investigator, to understand and comply with the requirements of the study
- 7. Meet surgical requirements/eligibility (including MRI scan within 3 months or at screening to confirm suitability for inner ear surgery)
- 8. Patients must weigh at least 40 kg to participate in the study, and must have a body mass index (BMI) <45 kg/m². BMI = Body weight (kg) / [Height (m)]²

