6.4.1 Auditory assessments

6.4.1.1 Pure tone audiometry

Hearing sensitivity to frequency-specific pure tone stimuli will be determined by measuring audiometric thresholds through earphones (air conduction) and bone-conduction vibrator (bone conduction) using a standard loudness bracketing procedure. The patient will be asked to respond when s/he hears the tone, and the softest sound detected will be defined as threshold for that tone. Immittance testing is completed as part of standard audiometric assessment.

- Air conduction thresholds will be measured for standard-frequency and extended-frequency ranges: 0.125, 0.25, 0.5, 1, 2, 3, 4, 6, 8, 10, 12.5, 14, 16 kHz.
- Bone conduction will be measured for frequencies 0.25 -4 kHz. Masking to determine ear-specific bone conduction thresholds will be performed when necessary.

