6.5.6 Hearing and balance assessments

The assessments for efficacy outlined in Section 6.4 will also serve as safety assessments.

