9.4.3 Handling of missing values/censoring/discontinuations

All missing data, which are missing due to an assessment not having been made, will be treated as "missing at random". Patients with partial data will be included in the primary analysis. Where a missing data value occurs, this will be set to missing in the analysis. For the combined baseline of screening and baseline data, where only screening or baseline data is available, this value will be taken as the baseline. If no pre-treatment data is available, the subject will be excluded from the analysis when comparing the change to pre-treatment values.

Pure tone audiometry values which are missing because the hearing threshold exceeded the upper limit of the machine will be imputed with the value of 5dB above the upper limit of the machine.

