9.4.4 Supportive analyses

Not applicable.

9.5

 Commercially Confidential

 Analysis of secondary
 Information
 variables

Secondary variables will be analyzed descriptively.

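### Tones not heard are scored as machine limit + 5 dB and averaged as measured values, so the change-from-baseline summary compresses change in both directions at frequencies near or beyond the limit

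*Protocol*

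**What the plan says.** Protocol 9.4.1 defines the variable: "The primary analysis variable is the audiometric threshold measured on a dB HL (hearing loss) scale at these frequencies", followed by 13 frequencies from 0.125 to 16 kHz. Protocol 9.4.2 analyses each frequency separately. It reasons that a tone not heard has a threshold above what the machine can deliver, and then substitutes a single number: "In this case the value will be imputed to 5dB above the upper limit of the machine". Protocol 9.4.3 restates this ("Pure tone audiometry values which are missing because the hearing threshold exceeded the upper limit of the machine will be imputed"), and SAP 7.1.2 and 7.1.3 carry the same rule.

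The change summary is in Protocol 9.4.2: "Change from baseline of the thresholds (mean of screening and baseline visit) will also be summarized by infusion volume, frequency, ear and visit/time". SAP 7.1.2 names only a listing and a graph for air conduction. The section headed "9.4.4 Supportive analyses" is marked not applicable. Protocol 6.4.1.1 describes threshold-finding as "using a standard loudness bracketing procedure" and gives neither the machine limit nor the step size. Protocol 6.5.6 gives audiometry a second role: "The assessments for efficacy outlined in Section 6.4 will also serve as safety assessments".

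**The concern.** By the protocol's own reasoning, a no-response result is a censored value: the threshold lies somewhere above the limit. Once limit + 5 is put in its place and averaged, a reader of the summary cannot tell a 5 dB shift from a response that disappeared. The limit is not stated, so an imputed value cannot be recognised from its size either.

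This matters because pure tone audiometry is a primary efficacy variable and also a safety measure, and Protocol 3.6.2 lists worsened hearing among the surgical risks. The population has severe-to-profound loss, so baselines near the limit are plausible. The entry rules do not prevent them. Criterion 3 in Protocol 4.1 reads "Minimal residual hearing based on the pure tone average of 0.5, 1, 2, and 4 kHz thresholds of ≤110 dB HL", so it bounds only an average of four frequencies. The other 13 − 4 = 9 frequencies have no upper entry bound.

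**Working it through.** **Inputs.** Scoring rule and baseline definition from Protocol 9.4.2; frequencies from 9.4.1; entry limits from 4.1. The machine limit L is not given, so results are stated relative to L. A 5 dB step is assumed. Positive change means worse hearing. The plan gives no figure of its own to reproduce.

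**Rule.** score(x) = x if x ≤ L, otherwise L + 5. Change = score(follow-up) − average of the two pre-treatment scores.

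**Largest recordable worsening at one frequency.**
- No response at both pre-treatment visits: (L + 5) − (L + 5) = 0 dB
- One visit at L, one no response: (L + 5) − (L + 2.5) = +2.5 dB
- Both visits at L: (L + 5) − L = +5 dB
- Both visits d dB below L: d + 5 dB

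**A true 20 dB loss** is recorded as +5 from L, +10 from L − 5, +15 from L − 10, and correctly as +20 from L − 15 or lower. **A true 20 dB gain** starting 10, 15 or 20 dB beyond L is recorded as −15, −10 or −5. Both directions shrink.

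**Single-ear sign errors.** I took every combination of two pre-treatment values and one follow-up on a 5 dB grid from L − 40 to L + 40 (17³ = 4,913). A true loss is never recorded as a gain. A true gain is recorded as worsening in 192. All 192 need pre-treatment values on opposite sides of the limit and at least 15 dB apart. Example: L and L + 15 before, L + 5 after. True change is (L + 5) − (L + 7.5) = −2.5; recorded change is (L + 5) − (L + 2.5) = +2.5.

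**Group mean.** Suppose all ears start d dB below L, a share p lose l dB, and the rest gain g dB.
- True mean = p·l − (1 − p)·g, positive when p > g/(g + l).
- Recorded mean = p·min(l, d + 5) − (1 − p)·g, negative when p < g/(g + min(l, d + 5)).
- Between those two shares, a true net loss is recorded as a net gain.

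Ten ears at L with g = 10 and l = 30: the bounds are 10/40 = 0.25 and 10/15 = 0.67, so 3 to 6 losers reverse the sign. With 5 losers the recorded mean is (5×5 − 5×10)/10 = −2.5 and the true mean is (5×30 − 5×10)/10 = +10.

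All patterns with g in {5, 10, 15, 20}, l in {10, 20, 30} and every possible number of losers from 1 to n − 1; entries count a true loss shown as a gain:

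| Baseline below L (dB) | 0 | 5 | 10 | 15 | 20 |
|---|---|---|---|---|---|
| Mean, n = 10 (108 patterns) | 28 | 12 | 4 | 2 | 0 |
| Median, n = 10 | 5 | 3 | 1 | 0 | 0 |
| Mean, n = 3 (24 patterns) | 8 | 1 | 1 | 0 | 0 |
| Median, n = 3 | 0 | 0 | 0 | 0 | 0 |

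**Can eligible ears reach the limit at the four averaged frequencies?** Assume no response counts as L + 5 in the entry average and the remaining frequencies sit at the 70 dB floor.
- L = 110: three no responses give (3×115 + 70)/4 = 103.75, eligible.
- L = 115: three give (3×120 + 70)/4 = 107.5, eligible.
- L = 120: two give (2×125 + 2×70)/4 = 97.5, eligible; three give (3×125 + 70)/4 = 111.25, not eligible.

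**The case against.** The strongest reply is that loss remains visible elsewhere. Every threshold is listed and plotted by patient, frequency and visit in a study of at most 22 patients. Auditory data are reviewed before dosing continues (Protocol 3.1), and the DSMB reviews audiometry directly (8.4). The study is described as non-confirmatory, and no visible test or decision rule uses this summary. All of that stands, and it confines the fault to the summary table.

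Several further limits also stand:
- Where no response is present both before and after dosing, the 0 dB is the instrument's limit. No scoring rule or count recovers further loss there; the value just should not be read as no change.
- Protocol 9.4.2 does not name the mean. A median and range may already be intended, and medians rarely reverse.
- The reversal patterns are artificial, with a common baseline, gain and loss.
- SAP 1.1 assigns table shells to Module 7 and derivations to Module 8. Neither was available, and either may hold a flag.
- Because SAP 7.1.2 plans only a listing and graph, production of the change table rests on the protocol alone.

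A reader might infer that the rule systematically hides hearing loss or favours the product. The documents do not support that: gains are compressed too, and the only single-ear sign errors on the 5 dB grid run from gain to recorded worsening. Nor do they support a claim that the 30 µL volume decision was affected, since audiometry was reviewed directly for that decision.

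What the objection does not remove is that the visible rule, followed as written, prints a response lost from the limit as an ordinary +5 dB change.

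**Conclusion.** The point holds as a minor reporting fault. At each frequency near or beyond the limit, the descriptive change summary compresses both loss and gain. A lost response is recorded as at most d + 5 dB from d dB below the limit, which is +5 dB at the limit itself. These caps follow from the rule for any limit.

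The wrong-sign means depend on constructed mixes of gains and losses with baselines within about 15 dB of the limit. They show what is possible and are not estimates of how often it happens. The real extent cannot be computed, because neither the limit nor the baseline distribution is given. The conclusion also assumes that Modules 7 and 8 do not already identify censored values.

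**What to change.** Keep limit + 5 for listings and plots, but flag each imputed value. In every change-summary row that holds a censored value:
- print the number at no response, the number going from response to no response, and the number going from no response to response, with mixed pre-treatment results counted separately;
- report median and range alongside any mean;
- mark the affected changes as censored, not measured.

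Show the study-ear lost-response counts with the safety results. If Module 7 or 8 already does this, it is enough to confirm it.

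The cost is one flag and a few count columns from data already collected, with no model and no new assessment. The downside is more output in small cells. The change table could run to 13 frequencies × 2 ears × 4 volumes × 4 post-dose visits = 416 rows, or 520 if visit 777 is shown separately. Printing counts only in affected rows limits this.
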